Safety monitoring by an independent Data Safety Monitoring Board has ceased following the results of the primary efficacy analysis of the Phase III study, GO28141. As with other vemurafenib studies, the risk for SCC will be mitigated by utilization of the Risk Management Plan (RMP) that is described in Section 5.3.4.6 of this protocol.

STUDY TREATMENT

Patients enrolled in a given cohort will receive vemurafenib and cobimetinib at a specified dose combination as described in Section 3. Vemurafenib will be dosed orally bid and cobimetinib will be dosed orally once daily. Study drug will be shipped in bulk to the study sites in bottles.

Patients in screening (written informed consent) for this study who were previously receiving 960 mg bid vemurafenib will be dose-reduced to 720 mg bid for 7–14 days prior to Cycle 1, Day 1 in Cohorts 1, 1A, 2, 2A, or 1C. Patients receiving 960 mg bid vemurafenib prior to screening initiation (written informed consent) and assigned to Cohorts 1B, 1D, 3, 4, or 5 will continue receiving 960 mg bid vemurafenib, assuming this dose has been adequately tolerated prior to starting the study. Patients in screening (written

informed consent) for this study who are treatment naïve to vemurafenib at the time of consent will only start vemurafenib on Cycle 1, Day 1 once they are deemed eligible for enrollment.

Vemurafenib will be dosed daily, and cobimetinib will be dosed on a 14/14, a 21/7, or a continuous daily schedule in a 28-day cycle.

On study visit days, the daily doses of cobimetinib will be taken in the clinic after pre-dose assessments have been performed. After establishing patient eligibility for continued administration of study drugs, patients will be given a sufficient number of tablets and/or capsules to last until the next visit. In some cases, extra tablets and/or capsules may be dispensed if there is a reasonable possibility that the patient's next visit may be delayed (e.g., due to inclement weather or distance of patient's home from study center).

Cobimetinib should be taken at approximately the same time each day, preferably in the morning, and no later than 4 hours after the scheduled time. Each dose of cobimetinib should be taken with a glass of water.

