1.2.2 Clinical Pharmacokinetics of Vemurafenib

Pharmacokinetic (PK) information is available for patients treated with 160 to 1120 mg twice daily (bid) of the optimized clinical formulation (also referred to as the micro-precipitated bulk powder [MBP] formulation). The MBP formulation has been provided as 40-mg capsules (dry granulation method), 80 mg capsules (wet granulation method), and 120-mg capsules (roller compaction method) in the PLX06-02 Phase I trial, a dose-escalation study in patients with metastatic melanoma.

The vemurafenib MBP formulations were developed to increase bioavailability. Dose-proportional increases were seen in exposure with the 40-, 80-, and 120-mg capsules, particularly from 240 to 960 mg bid. There were some patients who were high and low exposure outliers. The reason for this variability is currently unknown.

Steady-state exposure is expected to be reached by 15 days and mean steady-state levels of vemurafenib (area under the concentration–time curve [AUC_{0–24h}]) ranged from 428 µM·h to 1800 µM·h in the PLX06-02 Phase I trial. The 960 mg bid dose of vemurafenib achieved mean steady-state exposures of 90 µM and 1800 µM·h for maximum plasma concentration (C_{max}) and AUC_{0–24h}, respectively. The mean effective half-life of vemurafenib across all dose cohorts was ~50 hours (range of 30–80 hours).

Mean steady-state vemurafenib exposures (C_{max} and AUC_{0–8h}) achieved with the to-be-marketed 240-mg tablet formulation in the Phase II study, NP22657 (n=60), were found to be 11% higher compared with the 120-mg capsule formulation (PLX06-02, n=30) in metastatic melanoma patients dosed with 960 mg bid.

Additional information can be obtained from the vemurafenib IB.

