3.5 Rationale for Pharmacokinetic Evaluation Schedule

Vemurafenib and cobimetinib will be used in combination in metastatic melanoma patients for the first time in this study.

Historical PK data are available for both compounds as monotherapies. Data from the combination of both drugs used in this study will be compared with these historical controls to monitor any unexpected changes in pharmacokinetics that may occur following the co-administration of both drugs. Currently, no major concerns have been identified for any PK interaction between vemurafenib and cobimetinib. In vitro experiments indicate that vemurafenib may be a weak substrate and moderate inhibitor of Pgp. Cobimetinib is a substrate of Pgp and combination therapy with vemurafenib may lead to an alteration of plasma exposures of cobimetinib. Additional nonclinical and clinical data regarding the metabolism of vemurafenib suggest that the drug may be a mild inducer of CYP3A4. Preliminary information suggests that CYP3A and UGT2B7 are the enzymes responsible for cobimetinib metabolism. However, the fraction of cobimetinib metabolized by CYP3A is unknown. Thus, induction of CYP3A4 by vemurafenib may lead to decreased systemic exposures of cobimetinib.

In vitro CYP inhibition studies suggest that cobimetinib has a moderate potential to interact with drugs that are substrates for CYP2D6 (IC_{50} 1.8 μ M) or CYP3A (IC_{50} 5.9–1.7 μ M; K_i 7.6 μ M). It is unclear how cobimetinib may alter the pharmacokinetics of vemurafenib.

For patients who have progressed while receiving vemurafenib monotherapy immediately preceding enrollment in this trial only, an exposure time profile for vemurafenib will be taken at Day -1, spanning an 8-hour post-dose period to determine the exposure level of this drug prior to study start. Patients assigned to Cohorts 1, 1A, 2, 2A, and 1C who tolerated 960 mg bid vemurafenib prestudy will be dose reduced to 720 mg bid for at least 1 week prior to study start.

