11. FDG-PET imaging will be done at screening (≤ 14 days prior to Cycle 1, Day 1). If the patient has FDG-PET avid disease, he/she will undergo subsequent FDG-PET imaging. This will be scheduled once during mid-Cycle 1 (anytime between Days 10 and 14) and once on Cycle 2, Day 14 \pm 7 days to coincide with the first CT/MRI response assessment. FDG-PET scan must be performed fasting (patients must not have consumed any food or glucose/sugar-containing fluid) at least 4 hours prior to FDG-PET scan. Blood glucose level will be obtained immediately prior to FDG administration either by fingerstick test or by serum glucose assay on a blood sample obtained by venipuncture and processed in the local laboratory.
12. PK samples should be obtained according to the schedule provided in [Table 10](#) and [Table 11](#) for patients who progressed while on vemurafenib immediately prior to enrollment in this study and those previously untreated or treated (but without prior exposure to any BRAF or MEK inhibitor therapy) for locally advanced/unresectable or metastatic melanoma, respectively. Document date and time of all PK draws.
13. Patients who have progressed on vemurafenib will continue daily treatment with vemurafenib during the screening period pending cohort assignment. Confirm dose with study site monitor as a dose reduction may be required. During this study, patients will be treated with an oral dose of vemurafenib daily in a 28-day cycle. Patients available for enrollment in this study who were receiving 960 mg bid vemurafenib will be dose reduced to 720 mg bid for 7–14 days prior to enrollment in Cohorts 1, 1A, 2, 2A, and 1C. Patients assigned to Cohorts 1B, 1D, 3, 4, or 5 will continue receiving 960 mg bid vemurafenib throughout the screening period, assuming this dose has been adequately tolerated prestudy.

Table 9: Schedule of Assessments (All Cohorts Including Cobimetinib Monotherapy Cohort) (Cont.)

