21. For all patients—previously treated with vemurafenib and those either previously untreated or treated (but without prior exposure to any BRAF or MEK inhibitor therapy) for locally advanced/unresectable or metastatic melanoma—biopsies of accessible tissue are mandatory upon patient’s consent to participate in the trial. Fresh-frozen and paraffin-embedded tumor biopsy for molecular analyses will be obtained within 28 days of Cycle 1, Day 1 (unless progression biopsy tissue was submitted in previous study within 3 months of screening). Biopsies should be completed at least 48 hours before the initiation of study drug therapy on Cycle 1, Day 1. Biopsies (both formalin-fixed and fresh-frozen samples) will be collected at time of progressive disease. A biopsy of tumor tissue must be obtained during Cycle 1 while the patient is receiving cobimetinib; Day 10 to 14 is the required timing for this biopsy. It is highly recommended that the biopsy at disease progression be collected within 3 days after last study treatment. Lesions with the greatest change in dimensional size, based on interval evaluation, are the lesions to be biopsied. Excisional biopsies, punch biopsies, or multiple (2 or more), 14-gauge core needle biopsies are acceptable. **Fine needle aspiration (FNA) biopsies will not be accepted.**
22. For patients who develop any cutaneous lesion(s) suspicious for squamous cell carcinoma (SCC) or keratoacanthoma (KA) during treatment with vemurafenib and/or cobimetinib, biopsy tissue and a paired normal skin biopsy must be obtained for biomarker analyses (mandatory sample). Only one normal skin biopsy is required per patient, regardless of the number of SCC lesions identified and biopsied during the study. Suspicious lesions not thought to represent cutaneous SCC may also be sent for central pathological review at the discretion of the investigator and may undergo molecular characterization.

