5.5 Pharmacokinetic Assessments

Plasma samples for measurements of vemurafenib and cobimetinib concentrations and possible metabolites will be collected to characterize the pharmacokinetics of vemurafenib and cobimetinib.

For each PK blood sample collection, venous blood (2 mL in a heparin tube for vemurafenib and 3 mL in an EDTA tube for cobimetinib) will be collected to measure concentrations of vemurafenib and cobimetinib. When ECG recordings are obtained at the same visit, the collection of PK samples should be time-matched to the collection of ECG recordings (plasma samples collected after ECG recording) to investigate any potential relationship of systemic levels of vemurafenib and cobimetinib with ECG findings.

Plasma samples for the determination of vemurafenib and cobimetinib levels will be collected as outlined in [Table 10](#) and [Table 11](#) for patients who have progressed while receiving vemurafenib immediately prior to enrollment on this study and those either previously untreated or treated (but without prior exposure to any BRAF or MEK inhibitor therapy) for locally advanced/unresectable or metastatic melanoma, respectively. For cobimetinib, the sampling will allow determination of the total exposure (AUC_{0-24}), C_{max} , and C_{min} . For vemurafenib, plasma exposures will be assessed before (for patients previously treated with vemurafenib only) and during (all patients) co-administration with cobimetinib. Plasma concentrations will be compared with historical exposures observed in previous studies with vemurafenib.

Potential correlations of relevant PK parameters with dose, safety or efficacy outcomes, and other covariates will be explored.

Changes in PD markers will be listed by dose, exposure, cohort, mutation status, and response status. Additional PK and PD analyses will be conducted as appropriate.

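### In progressors cut from 960 to 720 mg bid before Cycle 1, the baseline PET or biopsy may precede the cut, so PD change can include a 25% lower vemurafenib dose

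*Combined protocol and SAP*

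**What the plan says.** **The reduction.** Progressors "previously receiving 960 mg bid vemurafenib will be dose-reduced to 720 mg bid for 7–14 days prior to Cycle 1, Day 1" if they enter Cohorts 1, 1A, 2, 2A or 1C (Synopsis, Study Treatment; Sections 3.4 and 6.1 agree). Those entering Cohorts 1B, 1D, 3, 4 or 5 stay on 960 mg bid if they tolerated it. The run-in is worded differently elsewhere. Section 3.5 has "will be dose reduced to 720 mg bid for at least 1 week prior to study start", with no upper limit, and Section 3.1.1 likewise sets only a one-week minimum. Table 9 footnote 13 has "dose reduced to 720 mg bid for 7–14 days prior to enrollment in Cohorts 1, 1A, 2, 2A, and 1C", which counts from enrollment.

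**Baseline PET.** "FDG-PET imaging will be done at screening", no more than 14 days before Cycle 1 Day 1 (Table 9 footnote 11; Section 5.3.5).

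**Baseline biopsy.** "Fresh-frozen and paraffin-embedded tumor biopsy for molecular analyses will be obtained within 28 days of Cycle 1, Day 1" (footnote 21), finished at least 48 hours before Cycle 1 Day 1. A progression sample from the prior study may be substituted if taken within 3 months of screening. Section 5.3.1, however, allows the biopsy only once eligibility is confirmed, and Section 4.2 requires eligibility laboratory results from the 2 weeks before first dose. Section 5.6.3.1 prefers, without requiring, that screening biopsies follow the PET.

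**PK.** In progressors, "an exposure time profile for vemurafenib will be taken at Day -1" (Section 3.5). Section 1.2.2 states "Steady-state exposure is expected to be reached by 15 days", a mean effective half-life of about 50 h (30–80 h), and dose-proportional exposure, particularly from 240 to 960 mg bid.

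**Use of PD.** "Changes in PD markers will be listed by dose, exposure, cohort, mutation status, and response status" (Section 5.5).

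**The concern.** The on-treatment PET and biopsy on Days 10–14 are taken on 720 mg bid plus cobimetinib. If the baseline was taken on 960 mg bid, the within-patient change has two parts: cobimetinib was added and the vemurafenib dose fell by a quarter. A progressor who stays on 960 mg has only the first part. A display of PD change by dose and cohort is then not like for like. Splitting patients by prior vemurafenib does not help, because the difference arises within the progressors.

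Footnote 13 makes this a practical possibility: progressors continue vemurafenib in screening until their cohort is known, and only then may a reduction be needed.

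At stake is a secondary objective, the PD effect of the combination by FDG-PET and paired biopsy (Section 2.1). To a much smaller degree it touches the primary objective of steady-state vemurafenib PK alone and in combination, because Day -1 falls at most 13 days after the cut.

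**Working it through.** **1. Reproduce the plan's steady-state figure.** Fraction of steady state after t hours = 1 − 2^(−t/t½). At 15 days (360 h): 99.3% for 50 h, above 99.9% for 30 h, 95.6% for 80 h. The stated 15 days reproduces at a 95% criterion.

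**2. Size of the dose change.** 720/960 = 0.75, a 25% lower dose. With proportional exposure, the 960-mg level is 960/720 = 1.333 times the 720-mg level.

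**3. Permitted baseline days still on 960 mg**, with the cut starting on the morning of Day -7 or Day -14:

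| Baseline | Permitted days | 7-day run-in | 14-day run-in |
|---|---|---|---|
| PET | Day -14 to -1 (14) | 7 (Day -14 to -8) | 0 |
| New biopsy, Section 5.3.1 governs | Day -14 to -2 (13) | 7 | 0 |
| New biopsy, footnote 21 window | Day -28 to -2 (27) | 21 (Day -28 to -8) | 14 (Day -28 to -15) |

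The second row assumes that confirming eligibility needs the laboratory results from within 2 weeks, so a new biopsy cannot fall before about Day -14. A substituted prior-study biopsy always precedes the cut. These are counts of allowed days. They are shares of patients only if tests are spread evenly over the window.

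**4. Day -1 PK.** With a 7-day run-in, Day -1 pre-dose is 6 × 24 = 144 h after the first 720-mg dose. A rough check: (1/3) × 2^(−144/50) = 0.333 × 0.136 = 4.5% above the 720-mg level. For the 8-hour profile, take a one-compartment model with doses every 12 h. Each dose D given s hours before the sampling day's morning dose adds D × (e^(−ks) − e^(−k(s+8)))/k, with k = ln 2/t½. Summed over doses:

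| Run-in | Result | t½ 30 h | t½ 50 h | t½ 80 h |
|---|---|---|---|---|
| 7 days | Day -1 AUC0–8h above 720-mg steady state | 0.9% | 3.8% | 8.6% |
| 7 days | Day 14/Day -1 ratio, no interaction | 0.991 | 0.963 | 0.925 |
| 14 days | Day -1 AUC0–8h above 720-mg steady state | 0.0% | 0.4% | 2.0% |
| 14 days | Day 14/Day -1 ratio, no interaction | 1.000 | 0.996 | 0.981 |

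**5. What a late baseline leaves behind.** On Day -2, the last permitted biopsy day, a 7-day run-in gives 5 × 24 = 120 h since the cut. The residual excess is (1/3) × 2^(−120/50) = 0.333 × 0.189 = 6.3% (2.1% at 30 h, 11.8% at 80 h), against 33% for a baseline on 960 mg.

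**The case against.** **The PD objective is the combination's effect, not cobimetinib's own.** This is true of the wording in Section 2.1. Even so, the change is measured from a vemurafenib baseline, and that baseline dose can differ between progressors now on the same regimen.

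**PD does not drive dose choice.** A reader might infer that dose selection is distorted. The documents do not support that. Section 3.1.4 lists adverse events, laboratory data, ECGs, dosing logs and PK for escalation, and safety, activity and PK for the recommended dose. Section 3.2 uses safety, activity and PK for the expansion schedule. PD is not named in either. PET is called a possible early readout of activity, but Sections 5.3.2 and 5.3.5 bar the Day 10–14 scan from response and disease-status decisions. This objection stands.

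**The biopsy exposure is smaller than footnote 21 suggests.** Reading that footnote alone, one might conclude that 52–78% of permitted days (14/27 to 21/27) precede the cut. If Section 5.3.1 governs, it is 0–54% (0/13 to 7/13). The two passages disagree, so both counts are given.

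**The needed dates largely exist.** Dose diaries, specimen dates and PK draw times are already collected. This stands, and makes the analysis part of the fix cheap. Section 18 also says that a clinical study report has been written, so the scheduling change helps only patients still to be enrolled.

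**Conclusion.** The gap is real for baseline PET and biopsy, and limited to progressors from 960 mg bid who enter Cohorts 1, 1A, 1C, 2 or 2A. With the shortest run-in, half the permitted PET days precede the cut; with the longest, none do. For a new biopsy the range is 0 to 7 of 13 days, or 14 to 21 of 27 if the 28-day window governs. Substituted biopsies always precede it.

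Two stronger readings are tempting and should not be drawn. First, that PD change is shown to be biased against the 720-mg cohorts: it could be understated there, but the documents give no dose-response for PET or pERK, and Sections 3.1.1 and 3.4 describe 720 mg bid as still effective. Second, that Day -1 PK still reflects 960 mg: it always follows the cut and mainly reflects 720 mg. It is about 4% high (1–9%) after 7 days and about 0.4% after 14, in a descriptive summary with no test or equivalence limit.

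The PK figures assume linear one-compartment kinetics and that the stated half-life range applies to the 240-mg tablet. The point is worth a cheap improvement; it does not undermine the design.

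**What to change.** No dosing change is proposed.

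1. In Table 9 footnotes 11 and 21 and Sections 5.3.5 and 5.6.3.1, add for patients whose vemurafenib is lowered in screening: take the already required baseline PET, and any newly taken baseline biopsy, after the reduction and as late as the 48-hour biopsy rule allows, PET first. Do not require a new biopsy where a prior-study sample is substituted.
2. From diary, scan and specimen dates, derive the vemurafenib dose and days on that dose at each baseline PET, biopsy and Day -1 profile. Show PD change separately for baselines taken before and after the reduction. Show the Day 14/Day -1 vemurafenib summary separately for patients with and without a recent dose change.
3. Reconcile the three run-in wordings (Synopsis with Sections 3.4 and 6.1; Sections 3.1.1 and 3.5; Table 9 footnote 13) and the two biopsy-timing wordings (footnote 21; Section 5.3.1).

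The cost is footnote and analysis wording, tighter screening logistics, and smaller subgroups in displays that are descriptive anyway. Item 2 can be applied to data already collected.

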1. BACKGROUND AND RATIONALE

1.1 Background

1.1.1 Melanoma

Approximately 160,000 new cases of melanoma are diagnosed globally each year [1]. According to a World Health Organization (WHO) report, about 48,000 melanoma related deaths occur worldwide every year [2]. The highest incidence rates of melanoma occur in Australia and New Zealand where the annual incidence is more than double the highest rates recorded in Europe. In Australia, melanoma represents the fourth most common cancer among males and the third most common cancer among females. Currently, the lifetime risk for development of melanoma in Australia is now 1 in 14 for men and 1 in 24 for women [3, 4]. In the United States, it is estimated that over 68,000 new melanoma cases will be diagnosed and over 8,000 patients will die from the disease during 2009. Further, incidence rates for melanoma have increased sharply by approximately 6% per year in the United States since the 1970s.

There are a limited number of treatments available for metastatic melanoma, and the response to available treatments to date has been extremely poor.

1.2 Role of BRAF Kinase in Melanoma

Recent advances in the understanding of the biology of melanoma have resulted in identifying the role of BRAF kinase in melanoma. Mutated BRAF dimers constitutively activate the RAS-RAF pathway leading to the generation of transcriptional signalling that promotes tumor growth. BRAF mutations in melanoma have been identified in 50%–68% of metastatic melanomas, specifically melanomas that arise from intermittent sun-exposed skin (e.g., in superficial spreading and nodular melanomas) [5, 6, 7, 8]. BRAF mutations are uncommon in acral, mucosal, and uveal melanomas. At the same time, BRAF mutations are common in benign nevi, suggesting that BRAF mutations are an early event in melanoma oncogenesis. About 90% of the BRAF mutations seen in metastatic melanoma occur in codon V600 and over 90% of the V600 mutations are V600E (1799 T>A) [9]. Other uncommon variants, such as V600K, V600R, and V600D (in order of decreasing frequency), have also been identified, primarily in melanoma. Nonclinical data indicate that these variant mutations, like V600E, result in constitutive activation of the BRAF kinase. Most of the transforming activity of the BRAF^{V600E} is thought to result through the constitutive activation of the mitogen-activated protein kinase (MAPK) pathway [10]. The therapeutic relevance of BRAF is supported by the demonstration that depletion of mRNA for oncogenic BRAF by siRNA leads to growth inhibition of melanoma cell lines in vitro [11, 12]. This has led to the development of agents that can inhibit BRAF kinase and tests to identify mutations [13, 14, 15].

The **cobas**[®] BRAF V600 mutation assay and Sanger Sequencing techniques have been utilized to identify BRAF^{V600} mutation status in clinical trials.

1.2.1 Study Drug Vemurafenib (BRAF Inhibitor)

Vemurafenib (also known as RO5185426 and PLX4032) is a low molecular weight, orally available inhibitor of the oncogenic form of the BRAF serine-threonine kinase

commonly found in metastatic melanoma. It is a potent and highly selective inhibitor of V600E-mutant BRAF.

Vemurafenib is currently approved as a treatment for adult patients with unresectable or metastatic BRAF^{V600} mutation–positive melanoma who have been diagnosed with the cobas[®] 4800 BRAF V600 Mutation Test in a number of countries worldwide, including the United States, Canada, members of the European Union, and numerous other countries worldwide.

